4.7 Efficacy Analyses

4.7.1 Primary Analysis

The efficacy endpoint will be the PD assessment of clotting time by WBCT; the efficacy endpoint will be summarized at observed time points and as change from baseline (and/or ratio) values using descriptive statistics and graphical presentations.

Change-from-baseline and percent-of-baseline will be calculated for all efficacy endpoints. Baseline for all efficacy endpoints will be defined as the pre-apixaban sample (pre-apixaban on the morning of Day 1).

The anticoagulant effect of apixaban will be evaluated by comparing WBCT measured at pre-PER977 (three hours post-apixaban on the morning of Day 4) versus baseline (pre-apixaban on the morning of Day 1). For the purposes of the efficacy analyses, subjects with percent-of-baseline WBCT at pre-ciraparantag $<120\%$ (i.e., $<20\%$ increase) will be considered as apixaban non-responders and will be excluded from all efficacy summaries and assessments.

Listings of individual efficacy variable collection times as well as derived sampling time deviations (where applicable), will be provided.

Individual observed and change from baseline values at scheduled time points and efficacy parameters will be listed and summarized by treatment. In addition, the nature of reversal of anticoagulation based on the definition of reversal of anticoagulation below using WBCT will be summarized and then listed for each subject.

Definition of Reversal of Anticoagulation

- Complete reversal is achieved for a treatment group if the mean WBCT is $\leq 110\%$

of baseline at any post-baseline time point up to and including 1 hour following test article administration. Complete reversal is achieved for a subject if WBCT is $\leq 110\%$ of baseline at any post-baseline time point up to and including 1 hour following test article administration.

- Complete and sustained reversal of anti-coagulation is achieved for a treatment group if the mean WBCT is $\leq 115\%$ of baseline at all time points between 1 and 5 hours (inclusive) following test article administration. Complete and sustained reversal of anti-coagulation is achieved for a subject if WBCT is $\leq 115\%$ of baseline at all time points between 1 and 5 hours (inclusive) following test article administration.

Statistically Significant Complete Reversal

- Statistically significant complete reversal, relative to mean placebo WBCT, is defined as $p < 0.05$, (one tailed) from the comparison of means between treatment and placebo at 15, 30, 45 minutes or 1 hour post study drug administration as measured by one-way Analysis of Variance (ANOVA) at study completion. Distribution diagnostics will be performed to assure assumptions associated with using ANOVA are met. The one-tailed Dunnett's test will be used for comparisons of treatment means.

Analysis of Means (ANOM) methods will also be used to compare means and variances across groups. These methods will be appropriate to test if any of the group means are statistically different from the overall mean or if the group standard deviations are statistically different from the root mean square error (RMSE).

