The pharmacodynamics results show that at pre-study drug on Day 3, mean observed WBCT after edoxaban dosing increased to similar levels in the placebo group and ciraparantag treatments. Over the one to six hours postdose interval (inclusive) after the first ciraparantag dose, complete reversal for WBCT was achieved in a higher percentage of subjects in the active treatments (82.9% for all doses) compared to the placebo group (60.0%). Across the 30 mg ciraparantag to 360 mg PER977 treatments, the rate of complete reversal at 30 mg was slightly lower (62.5%) while the rate was similar for 60 mg or higher dose levels (88.9% to 100%). Both evaluable subjects (100%) in the 15 mg PER977 treatment had partial reversal. None of the subjects in any of the placebo or active treatments had percent-of-baseline WBCT >190% at any time point (i.e., no reversal).

Results of statistical comparisons showed ciraparantag had no impact on re-anticoagulation with edoxaban as measured by WBCT at pre-study drug on Day 4 versus pre-study drug on Day 3. Over the 1 to 6 hour postdose interval (inclusive) after the second ciraparantag dose on Day 4, the rates of complete reversal were comparable to Day 3. Overall, 88.6% of the subjects in the active ciraparantag treatments and 53.3% of subjects in the placebo group had complete reversal. Across the 30 mg to 360 mg active treatments, the rate of complete reversal was slightly lower (66.7%) for 180 mg while the rate was similar for all other dose levels (87.5% to 100%). None of the subjects in any of the placebo or active treatments had percent-of-baseline WBCT >190% at any time point (i.e., no reversal).

Treatment comparisons of percent-of-baseline WBCT showed lower values compared to placebo following 60 mg to 360 mg ciraparantag on Day 3 that were statistically significant at most time points between five minutes to three hours after the end of injection (geometric least-squares [LS] ratios ranged from 86.52% to 93.70%); and following 30 mg to 360 mg ciraparantag on Day 4 at most time points between five minutes to six hours after the end of injection (geometric LS ratios ranged from 84.91% to 95.71%). On both study days, WBCT at different dose levels in the active ciraparantag treatments returned to baseline within the 0.083-hour to 0.75-hour time points. Post-baseline WBCT in placebo-treated subjects did not decrease to baseline level until the 1-hour (Day 4) to 1.5-hour (Day 3) post-study drug time point.

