## 9.8 Analysis of the Primary PD Endpoint (WBCT)

### Definition of Reversal of Anticoagulation

- Complete reversal is achieved for a treatment group or for a subject if the mean WBCT is  $\leq 110\%$  of baseline at any post-baseline time point up to and including 1 hour following test article administration. Complete reversal is achieved if WBCT is  $<=110\%$  of baseline at any post-baseline time point up to and including 1 hour following test article administration
- Complete and sustained reversal of anti-coagulation is achieved for a treatment group if the mean WBCT is  $\leq 115\%$  of baseline at all time points between 1 and 5 hours (inclusive) following test article administration. Complete and sustained reversal of anti-coagulation is achieved for a subject if WBCT is  $\leq 115\%$  of baseline at all time points between 1 and 5 hours (inclusive) following test article administration

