### Statistically Significant Complete Reversal

- Statistically significant complete reversal, relative to mean placebo WBCT, is defined as  $p<0.05$ , (one tailed) from the comparison of means between treatment and placebo at 15, 30, 45 minutes or 1 hour post study drug administration as measured by one-way Analysis of Variance at study completion. Distribution diagnostics will be performed to assure assumptions associated with using ANOVA are met. Analysis of Means (ANOM) methods will be used to compare means and variances across groups. These methods will be appropriate to test if any of the group means are statistically different from the overall mean or if the group standard deviations are statistically different from the root mean square error (RMSE). Tukey HSD multiple comparison procedure will be used to test for all pairwise differences among the means (Tukey 1953, Kramer 1956). This test is an exact alpha-level test if the sample sizes are the same, and conservative if the sample sizes are different (Hayter 1984).

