As of August 15, 2016, ciraparantag has been evaluated in four clinical studies of single escalating doses of ciraparantag following administration edoxaban (PER977-01-001; NCT01826266), unfractionated heparin (PER977-01-002; NCT02206087), and enoxaparin (PER977-01-003; NCT02206100), and following anticoagulation and re-anticoagulation with edoxaban (PER977-02-001; NCT02207257, see protocol section 1.2). These studies have shown that, a single intravenous (IV) dose of ciraparantag demonstrated reversal of anticoagulant drug (e.g. edoxaban and enoxaparin) induced anticoagulation for different testing periods following study drug administration.

This phase 2 study is intended to extend the findings of efficacy, safety and pharmacokinetics (PK) characteristics of the study drug, ciraparantag; a randomized, single-blind, placebo-controlled assessment of the efficacy and safety of ciraparantag administered to healthy volunteers measuring clotting times using WBCT is an acceptable study design. Further data on efficacy, safety, tolerability, and PK characteristics will be collected.

A total of three dosing cohorts (Cohorts 1-3) are planned. The planned doses of ciraparantag or placebo (administered as a volume equivalent of ciraparantag) have been evaluated as single and repeat IV doses from 5 mg ciraparantag acetate (3 mg ciraparantag) up to 600 mg ciraparantag acetate (360 mg ciraparantag) in previous protocols (PER977-01-001, PER977-01-002, PER977-01-003, and PER977-02-001).

The goal of the study is to explore the dose range of ciraparantag that reverses the anticoagulation induced by therapeutic doses of apixaban at steady state. The study is intended to establish a dose of ciraparantag that fully reverses steady-state apixaban, to evaluate at least one dose above the reversal dose to establish a therapeutic index, and at least one partial or no effect dose.

This statistical analysis plan (SAP) covers the detailed procedures for performing statistical analyses and for producing tables, listings, and figures (TLFs) in the study.

2 Study Objectives

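### The definition of statistically significant complete reversal omits the 110%-of-baseline threshold, so as written a dose with only a partial effect can earn the label

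*SAP*

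**What the plan says.** SAP 4.7.1 first gives the threshold definitions. For a group: "Complete reversal is achieved for a treatment group if the mean WBCT is" no more than 110% of baseline at one or more time points in the first hour after study drug. Protocol 9.8 has the same criterion: "Complete reversal is achieved for a treatment group or for a subject if the mean WBCT is" at or below that level. Complete and sustained reversal is defined separately, by a 115% limit from 1 to 5 hours.

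A new heading then introduces the test: "Statistically significant complete reversal, relative to mean placebo WBCT, is defined as" a one-tailed p below 0.05. In protocol 9.8 this p-value comes from the "comparison of means between treatment and placebo at 15, 30, 45 minutes or 1 hour post study drug administration", by one-way ANOVA, and the SAP has the same comparison. The SAP adds: "The one-tailed Dunnett's test will be used for comparisons of treatment means". SAP 4.11 records only that Dunnett's test replaced Tukey's procedure. No threshold appears under this heading in either document.

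The stated goal (SAP 1, Introduction) is to find a fully reversing dose, and to "evaluate at least one dose above the reversal dose to establish a therapeutic index, and at least one partial or no effect dose". Protocol 9.7 lists partial and complete reversal as different categories.

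**The concern.** A p-value against placebo shows that a dose lowers clotting time. It does not show that clotting time is back near baseline. Complete reversal is a statement about the second, and the definition tests only the first. A dose that takes WBCT from 140% to 125% of baseline is by the plan's own threshold not a complete reversal. If the difference is significant at any of the four times, the sentence as written still lets the report call it a statistically significant complete reversal. This is the only definition under the SAP's primary analysis that tests each dose against placebo, so its label is likely to be the one cited. A programmer working from the text would have to guess whether the threshold applies.

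**Working it through.** **Side by side.** The group definition (SAP 4.7.1, protocol 9.8) has a threshold and no test. The significance definition in the same sections has a test, no threshold and no cross-reference to the threshold. A dose can meet the second without meeting the first.

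**Inputs from the documents.** There is no sample-size or power figure to reproduce (SAP 3.4). Each cohort has 16 subjects randomised 3:1, so 16 x 3/4 = 12 active and 4 placebo. Placebo is pooled over three cohorts (SAP 3.5), so 3 x 4 = 12. ANOVA degrees of freedom are 48 - 4 = 44.

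**Inputs assumed.** The documents give no SD, placebo course or correlation between times, and do not say whether raw WBCT or percent of baseline is tested. Assumed: percent of baseline, SD 12, 15 or 20 points, equal correlation 0.5 or 0.8 between the four times, normal data.

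**Smallest difference that earns the label.** The one-sided Dunnett critical value for three doses against control, 12 per group, 44 df, is 2.12. The required observed difference is 2.12 x SD x sqrt(2/12) = 0.865 x SD:

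- SD 12: 10.4 points
- SD 15: 13.0 points
- SD 20: 17.3 points

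With placebo at 140% and SD 15, an observed dose mean of 140 - 13.0 = 127.0% qualifies, which is 17 points above the threshold.

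**How often this could happen.** Simulation, 20,000 trials per setting, with the variance pooled over the four groups at each time. Mislabelled means that the label is earned while the dose-group mean is above 110% at all four times. The last column is the rule proposed under the fix (threshold met at some time, significance at some time). It equals the current rule minus the mislabelled trials, setting by setting. Means are constant over time.

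| True mean, dose vs placebo | Label under current wording | Of all trials, mislabelled | Label with threshold added |
|---|---|---|---|
| 125% vs 140% | 59-98% | 57-98% | 0-2% |
| 120% vs 130% | 34-79% | 26-78% | 1-11% |
| 115% vs 120% | 15-35% | 3-20% | 11-17% |

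The labels left in the last row arise because a true 115% mean can by chance be observed at or below 110% at one of four times. That belongs to the plan's any-time definition, not to the missing threshold.

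**What the threshold costs a dose that does reverse.**

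- True mean 105% at all times: declared in 92-99% of trials against placebo 140%, a loss of up to about 8 percentage points. Against placebo at 130%, 125% and 120% the loss is at most about 5, 3 and 1 points.
- Placebo falling 140, 130, 120, 110% and dose falling 120, 115, 110, 105%: current wording declares in 66-98%, the threshold rule in 60-93%, a loss of about 6 to 8 points.
- Same falling case, with threshold and significance required at the same time point: 26-43%, a loss of about 40 to 58 points.

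**The case against.** The strongest reply is that the threshold was meant all along. Complete reversal is a defined term, given just above the test, and SAP 4.11 describes the procedure as the statistical analysis of complete reversal, which suggests a test attached to a state already defined. On that reading only a cross-reference is missing. This may well have been the intent, but the sentence defines the whole phrase by the p-value and does not say so.

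The second reply is that little depends on the label. The reversal categories are still summarised by treatment and listed by subject (protocol 9.7, SAP 4.7.1), so a careful reader would see the mismatch. This stands, and it limits the harm.

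Three stronger readings are tempting and are not supported:

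- A reader might infer from protocol 1.2.4 that partial-effect doses have already passed such a test, since significant Day 3 "geometric least-squares [LS] ratios ranged from 86.52% to 93.70"%. The same section says that WBCT on active treatment returned to baseline between 0.083 and 0.75 hours, and it gives no placebo percent-of-baseline level to pair with the ratios. They also extend to three hours, beyond this rule's window. They do not show a partial-effect dose earning the label.
- A reader might infer that dose selection between cohorts would go wrong. The protocol synopsis ties escalation and de-escalation to the 115% sustained criterion, not to this label.
- A reader might infer that threshold and significance must hold at the same time point. The documents define group reversal at any time in the first hour, so that link would be a new and stricter rule.

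**Conclusion.** The point holds as a defect of wording. As written, both documents allow a dose whose mean stays above 110% of baseline to be reported as a statistically significant complete reversal. This conclusion rests on the text alone. The simulated rates, from 3% to 98% depending on the setting, rest wholly on assumed SD, correlation, placebo level and analysis scale. They show that the gap can matter at this sample size, not how likely it is in this trial. The consequence is limited to a wrong efficacy label on the primary endpoint. It should be corrected because the label blurs the distinction between full and partial reversal that the study is meant to draw, and because the correction is cheap.

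**What to change.** Replace the definition in SAP 4.7.1 with wording such as:

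> Statistically significant complete reversal is declared for a dose when (i) the dose group meets the complete-reversal definition above, that is, mean WBCT at or below 110% of baseline at one or more time points up to 1 hour, and (ii) the one-tailed Dunnett-adjusted p-value against pooled placebo is below 0.05 at 15, 30 or 45 minutes or 1 hour. A dose that meets only (ii) is reported as having WBCT significantly lower than placebo.

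Align protocol 9.8. The change needs one sentence in each document, one condition in the program and no new data. A dose that meets only (ii) keeps its result under an accurate name.

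The sponsor may choose to require (i) and (ii) at the same time point. That is an option and not part of this correction, and the large loss in the falling-placebo case should be weighed first.

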2.2 Secondary Objectives

The secondary objectives of this study are:

- To evaluate the safety and tolerability of ciraparantag 60 mg (100 mg ciraparantag acetate), 120 mg (200 mg ciraparantag acetate), and 30 mg (50 mg ciraparantag acetate), and additional cohorts if necessary administered approximately 3 hours after 10 mg apixaban administration at steady state.

- To assess the PK characteristics of apixaban and of ciraparantag and its primary metabolite, 1,4-bis(3-aminopropyl) piperazine (BAP).

[figure not shown]
3 Study Design and Methods

This is a randomized, single-blind, placebo-controlled assessment of the efficacy and safety of ciraparantag administered to healthy volunteers measuring clotting times using WBCT. All subjects will undergo screening up to 36 days prior to enrollment.

Randomization will take place on Day 4 after administration of apixaban. Subjects will be enrolled sequentially into one of up to three cohorts. If the Screening visit takes place within 3 weeks prior to check-in, the check-in procedures may be modified to exclude redundant procedures at the discretion of the Investigator. There will be a safety review after completion of treatment in one cohort and before initiation of treatment in the subsequent cohort.

Subjects (n=16 per cohort) will be randomized in a 3:1 ratio to receive ciraparantag or placebo (saline for injection). [Figure 1](#) depicts the experimental design.

Figure 1 Dose Schema

All subjects will receive 10 mg apixaban for 3.5 days (twice daily Q12 on Days 1-3 and once on the morning of Day 4). On Day 4, approximately 3 hours after administering apixaban, study drug or placebo will be intravenously administered. Study drug will be administered only to those subjects who have a minimum increase in clotting time of 20% (as measured by WBCT) above Day 1 pre-apixaban baseline levels at the pre-study drug time point on Day 4 (i.e., 2.75 hours post-apixaban). Any subject who does not have a minimum increase in clotting time of 20% above Day 1 pre-apixaban baseline levels at the pre-study drug time point on Day 4 will be discontinued from the study and replaced. At approximately 3 hours following apixaban a single IV dose of study drug (ciraparantag or placebo) will be administered.

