4.11 Changes from Pre-Specified Analyses

In the statistical analysis of complete reversal, Tukey HSD multiple comparison procedure was replaced by one-tailed Dunnett's test for comparison of treatment and placebo means.

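### The test of complete reversal can succeed at any of four time points, but Dunnett adjusts only across doses, so the familywise one-tailed error exceeds 5% (about 9-17% at assumed between-time correlations of 0.9-0.3).

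*SAP*

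**What the plan says.** In SAP 4.7.1 the label is set at one-tailed p<0.05 "from the comparison of means between treatment and placebo at 15, 30, 45 minutes or 1 hour post study drug administration", by one-way ANOVA once the study is complete. The multiplicity procedure is given in one sentence: "The one-tailed Dunnett's test will be used for comparisons of treatment means". SAP 4.11 records where it came from: "Tukey HSD multiple comparison procedure was replaced by one-tailed Dunnett's test for comparison of treatment and placebo means". Protocol 9.8 has the same four time points joined by the same *or*, with Tukey HSD for pairwise group differences.

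Neither document names a primary time point, a testing order, a repeated-measures model or a split of alpha over time. The preceding definition of complete reversal in SAP 4.7.1 is met by a group mean of at most 110% of baseline at any time point up to 1 hour. That supports reading the *or* as any one of the four.

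**The concern.** A one-way ANOVA has treatment as its only factor, so the four time points mean four ANOVAs. Dunnett protects the three dose-versus-placebo comparisons inside each one. A dose that misses at 15 minutes can still earn the label at 30, 45 or 60 minutes, at no cost in alpha. By adopting Dunnett, the plan chose to control the chance of any false claim across doses. The rule as written does not hold that chance at 5%.

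The comparison with placebo matters because the 110% and 115% definitions have no comparator and WBCT falls without drug. Protocol 1.2.4 reports that 60.0% (Day 3) and 53.3% (Day 4) of placebo subjects met that edoxaban study's own criterion for complete reversal. SAP 2.1 makes reversal assessed by WBCT the sole primary objective, and this is the only planned test of WBCT between treatment and placebo.

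**Working it through.** **Inputs from the documents**
- Doses: SAP section 1 states "A total of three dosing cohorts (Cohorts 1-3) are planned".
- Group sizes: SAP section 3 states "Subjects (n=16 per cohort) will be randomized in a 3:1 ratio to receive ciraparantag or placebo". That is 12 active and 4 placebo per cohort. SAP 3.5 pools placebo across cohorts, so placebo n = 3 × 4 = 12.
- Error df for four groups of 12: 48 − 4 = 44.
- Alpha 0.05, one-tailed; four time points.

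**Assumed:** normal data, equal variances, complete data, and the correlation rho between time points within a subject. Neither document gives rho.

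**Step 1. Reproduce the nominal 5% at one time point.** The statistic for dose d is t = (placebo mean − dose mean) / (s × √(2/12)). Two contrasts share the placebo group, so their correlation is 0.5. Solving P(max of three t ≤ c) = 0.95 with 44 df gives c = 2.12. Familywise error is 5.0%, and the error for one named dose is about 2.0%.

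**Step 2. Bound the error over four time points.** If the time points were independent: 1 − 0.95⁴ = 18.5%. If perfectly correlated: 5%.

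**Step 3. Simulate between the bounds.** No drug effect, cut-off 2.12 at each time point, 100,000 to 200,000 trials per setting, equal correlation rho:

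| rho | At least one of three doses significant | One named dose significant |
|---|---|---|
| 0 | 18.6% | 7.8% |
| 0.3 | 16.6-16.9% | 7.1% |
| 0.5 | 15.0% | 6.4% |
| 0.7 | 12.7% | 5.4% |
| 0.8 | 11.2% | 4.7% |
| 0.9 | 9.1-9.2% | 3.8% |
| 0.95 | 7.9% | 3.2% |
| 0.99 | 6.2% | 2.5% |

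The excess of 18.6% over 18.5% at rho 0 is simulation error. If correlation instead decays with distance in time (lag-1 correlation 0.5, 0.7, 0.8, 0.9, 0.95), the familywise error is 16.1, 14.1, 12.3, 10.2 and 8.6%.

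**Step 4. Check the remedies.**
- Dunnett at 0.05/4 = 0.0125 per time point (c = 2.72): familywise error 5.0, 4.7, 4.3, 3.7 and 2.6% at rho 0, 0.3, 0.5, 0.7 and 0.9.
- One max-t cut-off over the 3 × 4 = 12 contrasts: about 2.72, 2.67, 2.65, 2.57 and 2.42 at the same rho values.
- Dunnett at 0.05 on each subject's four-point mean: 4.8-5.1% at every rho tried.

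**Step 5. Per-dose power for a constant 1 SD effect at rho 0.7.** At one time point the noncentrality is 1/√(2/12) = 2.45, giving 63%. The four-point mean has variance (1 + 3 × 0.7)/4 = 0.775, so the noncentrality is 2.45/√0.775 = 2.78, giving 74%. By simulation, max-t gives 70% and the unadjusted rule 84%.

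**The case against.** **The joint reading.** The label follows directly after the 110% definition, and a reader might take it to require both p<0.05 and a group mean of at most 110% of baseline. Only subjects at 120% or more of baseline are dosed, so an inert drug might rarely meet both. With an assumed SD of 12 points and rho 0.3-0.9, the joint rule gives 9-17% if the null mean is 105-110% of baseline, 7-12% at 115% and about 1% at 120%. With an assumed SD of 20 it is 5-9% at 120%. So the joint reading could remove the inflation, but only if WBCT stays high without drug. SAP 4.7.1 defines the label by the p-value alone. What stands is that the wording needs settling.

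**Phase 2 dose exploration.** SAP 3.4 reports no formal sample size calculation, and neither document states a familywise 5% in words. This lowers the consequence. It does not change the arithmetic, and replacing Tukey with Dunnett was itself a multiplicity decision.

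**Four stronger readings a reader might infer, which the documents do not support:**
- That each dose carries a 9-17% error. That range is for at least one of three doses; one named dose has about 4-7% at rho 0.9-0.3.
- That 9-17% is a known figure. It rests on an assumed correlation. Four samples from one subject within 45 minutes could correlate above 0.9, which gives a smaller excess.
- That this p-value drives dose decisions during the trial. The protocol synopsis (Statistical Methods) ties escalation or de-escalation to the descriptive 115% rule over 1-5 hours, Protocol 5.9 gives the decision to a review group, and the ANOVA is run at study completion.
- That this is the only hypothesis test of WBCT. SAP 4.7.1 also plans Analysis of Means, but against the overall mean rather than placebo.

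**Conclusion.** The concern holds as a statement about familywise error. As written, the rule exceeds its nominal one-tailed 5% at any between-time correlation below 1: about 9-17% at 0.9-0.3, with limits of just above 5% and about 18.5%. This assumes 12 per group, pooled placebo, Dunnett applied separately at each time point, and the label defined by p alone. It affects the final efficacy claim by dose and leaves the cohort escalation rule untouched.

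**What to change.** Amend SAP 4.7.1 before the final WBCT comparison is run, in one of two ways:

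1. **Keep the any-time-point rule** and make one adjustment over all 12 dose-by-time contrasts. Use either a max-t critical value estimated from the observed correlation (about 2.4-2.7 instead of 2.12), or Dunnett at 0.0125 per time point, which is simpler but conservative when correlation is high.
2. **Name one confirmatory test** under the planned one-tailed Dunnett at 0.05, with the other time points descriptive. This could be each subject's mean WBCT over 15, 30, 45 and 60 minutes, or the 1 hour value. The 1 hour option needs a stated rule for combining the triplicates, because SAP 4.7.2 assigns them only to inter-observer variability.

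In either case, state whether the label also requires a group mean of at most 110% of baseline at the same time point.

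The cost is SAP wording, with no new data or subjects, and a somewhat stricter bar. In the Step 5 setting, per-dose power is about 70% (max-t) or 74% (four-point mean), against 84% for the unadjusted rule. The four-point mean also changes the question, from reversal at some point in the first hour to average effect over it. If the sponsor wants to keep the first question, option 1 fits better.
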